RSV LRTI analysis: For the proportion of subjects with a medically attended RSV infection, only those RSV hospitalizations meeting the protocol-specified definition of LRTI (a subset of all RSV hospitalizations) will be counted towards the hospitalization component; the outpatient component will remain as described for the primary analysis.

Alternative LRTI Definition Analysis: Comparing the proportion of subjects with a medically attended RSV-confirmed infection (hospitalization or outpatient lower respiratory tract infection) during the study period (Day 150) as compared to placebo; using the following definition of LRTI:

- Infant with RSV-proven infection who presents with cough or difficulty breathing and 2 of the following criteria:
  - Lower chest wall indrawing
  - Hypoxemia (peripheral capillary oxygen saturation <95% breathing room air)
  - Wheezing or crackles
  - Ventilatory failure (needing ventilator support in any form)
  - New onset apnea
  - Increased respiratory rate using WHO criteria for fast breathing for age

The primary endpoint events of medically attended RSV infection (hospitalization or outpatient LRTI) will also be analyzed by stratified logistic regression and by stratified log-rank test and presented using a Kaplan-Meier curve. For the log-rank test and Kaplan-Meier curve, time to the first primary endpoint event will be analyzed; subjects who do not have a primary endpoint event will be censored at the last time point when the primary endpoint event is assessed.

Additional sensitivity analyses are planned to support the primary analysis, including exact test method (Fisher's), etc. All sensitivity analyses with associated details will be described in the SAP.

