$$v_{\phi} = \frac{\sum w_h^2 \left(\frac{p_{1h}^* (1 - p_{1h}^*)}{n_{1h} + 1} + \frac{p_{2h}^* (1 - p_{2h}^*)}{n_{2h} + 1} \right)}{2}$$

where

$$p_{1h}^* = \frac{e_{1h} + \phi \times n_{1h} + 0.5}{n_{1h} + 1}, \quad p_{2h}^* = \frac{e_{2h} + \phi \times n_{2h} + 0.5}{n_{2h} + 1}$$

The 95% asymptotic CI of ϕ is $[\phi - z_{0.975} * v_{\phi}, \phi + z_{0.975} * v_{\phi}]$ where $z_{0.975}$ is the 98.75th percentile of the standard normal distribution. The p-value will be computed from the z-score = ϕ / v_{ϕ} . A SAS macro will be used to calculate all the above statistics.

In addition to the absolute risk difference, the stratum-adjusted relative risk of the primary efficacy variable will be provided for the pairwise comparisons of each REGN2222 treatment arm to placebo for descriptive purpose. The number of subjects with primary endpoint event(s)

stratum-specific relative risks will be combined based on the MH method to compute the point estimate and asymptotic 95% CI of stratum-adjusted relative risk using the SAS FREQ procedure. In the event that there are zero table cells in any strata, the exact CI for the relative risk may be computed in lieu of the asymptotic CI by specifying the RELRISK option in the EXACT statement of the SAS FREQ procedure.

The statistical testing of the 2 pairwise comparisons of each REGN2222 treatment arm to placebo for the primary measure will be evaluated at a 2-sided significance level of 0.05 per pairwise comparison, adjusting for multiplicity through a hierarchical inferential approach. In the hierarchy testing sequence, the comparison of REGN2222 2 doses arm to placebo is the first pairwise treatment comparison, and the comparison of REGN2222 1 dose arm to placebo is the second pairwise treatment comparison.

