5.7.1.3. Sensitivity to the Handling of Missing Data

The following analyses will be conducted to assess the results from the primary analysis with regards to the handling of missing data. As appropriate, p values will be provided for descriptive purpose only.

Observed-Case Analysis

In the observed-case analysis, for each treatment group, the proportion of subjects considered to have primary endpoint event occurrence will be calculated with the numerator being the number of subjects with observed primary endpoint event(s) (including ET subjects who had their primary endpoint missing but died prior to Day 150 due to causes adjudicated to be RSV related), and the denominator being the number of subjects in the FAS. The observed-case based proportion difference will be calculated for each stratum h and then combined across strata to generate the CMH statistics following the same method as in the primary approach.

Tipping Point Analysis

A tipping point analysis will be employed to explore the degree of shift from the placebo event rate used in the imputation of missing data in REGN2222 arms. The tipping point analysis will include the following steps to impute missing primary endpoint at Day 150 visit:

1. Subject deaths prior to Day 150 that are adjudicated to be RSV related will be included as "event occurred".
2. Remaining early termination subjects (including non-RSV deaths) in the **placebo** group will be imputed to the average placebo score (ie, the KM estimate of the primary endpoint event rate in all subjects randomized to the placebo group).
3. Remaining early termination subjects (including non-RSV deaths) in the **REGN2222** arm will be imputed to $\delta \times n_{ih} \times \theta_{ih} / g_{ih}$, where $\delta = 2$. (Note: $\delta = 1$ is equivalent to the primary analysis)

4. Repeat the step 3 with $\delta = 3, 4, 5$, etc. until reaching the point that the treatment effect of REGN2222 will be lost (ie, the difference [REGN2222 – placebo] in the proportion of subjects with primary endpoint event[s] is ≥ 0).

The tipping point analysis will be conducted for the pairwise comparisons of each REGN2222 arm to placebo separately, using the same CMH statistics as in the primary approach.

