5.7.3. Adjustment for Multiple Comparison

To control the 5% overall Type I error for the 2 pairwise comparisons in the primary analysis, the overall study α level will be controlled by the use of a hierarchical inferential approach.

Statistical significance of the first pairwise treatment comparison (REGN2222 2 doses arm to placebo) is required before drawing inferential conclusions about the second pairwise treatment comparison (REGN2222 1 dose arm to placebo) at the 0.05 alpha level. This fixed hierarchical approach will ensure a strong control of the overall Type I error rate at the 0.05 level for each REGN2222 dose regimen comparison.

Further, in the case that the primary efficacy endpoint is statistically significant at 0.05 (2-sided) alpha level for both pairwise treatment group comparisons specified in the above paragraph, the secondary efficacy endpoint will be tested using the same hierarchical inferential approach as used for the primary efficacy endpoint.

This multiple testing procedure ensures a strong control of the overall Type I error rate at the 0.05 level. No further adjustments will be made for other analyses for which p-values will be provided for descriptive purpose only.

No adjustment will be made for the first step and second step statistical analyses (Section 8), since the primary and secondary efficacy endpoints will have been concluded at the time of the first step analysis.

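### The tipping-point analysis stops when the point estimate reverses, not when significance at 2-sided 0.05 is lost, so its labelled point lies beyond the shift that overturns the conclusion

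*SAP*

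**What the plan says.** SAP 5.7.1.3 keeps placebo dropouts at the placebo Kaplan-Meier rate and imputes REGN2222 dropouts at a shifted rate, with δ = 2, then 3, 4, 5 and so on, "until reaching the point that the treatment effect of REGN2222 will be lost". It spells this out as the point where the REGN2222 minus placebo difference "in the proportion of subjects with primary endpoint event[s] is ≥ 0". No p-value or confidence limit enters the rule. Each step is run "using the same CMH statistics as in the primary approach", and for the section as a whole: "As appropriate, p values will be provided for descriptive purpose only".

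The trial's conclusion rests on a different criterion. Under SAP 5.7.1 each comparison "will be evaluated at a 2-sided significance level of 0.05 per pairwise comparison", and "The p-value will be computed from the z-score". Under SAP 5.7.3, "Statistical significance of the first pairwise treatment comparison (REGN2222 2 doses arm to placebo) is required before drawing inferential conclusions" about the single-dose arm. Protocol 9.5.2.1 leaves the specification to the SAP: "All sensitivity analyses with associated details will be described in the SAP".

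**The concern.** A tipping-point analysis should show how unfavourable the missing-data assumption must become before the trial's conclusion no longer holds. Here the conclusion is statistical significance, but the labelled point is reversal of the estimate. A reader given that δ as the tipping point would credit the result with more robustness than it has.

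No other planned analysis fills the gap. The primary analysis imputes REGN2222 dropouts at the placebo rate. The observed-case analysis keeps them in the denominator as non-events. The time-to-event analyses (SAP 5.7.4) censor them. Only the tipping-point analysis assumes anything worse than the placebo rate for REGN2222 dropouts.

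A second problem is that the readable text puts no upper limit on δ times the placebo rate. Where reversal would need an imputed rate above 1, the SAP does not say when the loop ends or what is reported.

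**Working it through.** **Inputs.** From SAP 2.2: placebo rate 10%, REGN2222 rate 4%, about 1200 treated infants (1200/3 = 400 per arm) and 5% dropout. The 5% is stated for the original design only; I assume it for the reduced one. Other rates and dropout levels below are assumptions chosen to show a range.

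**Plan's own figures first.** The continuity-corrected chi-square formula at 2-sided 0.025 and 90% power gives 480 per arm, and 480/0.95 = 505.3, against 505 stated. At 2-sided 0.05 it gives 87.4% power with 380 per arm (400 less 5%), against about 87% stated. The planning inputs are therefore read correctly. The SAP gives no δ to reproduce.

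**Direction.** With m1 of n1 REGN2222 outcomes missing and placebo rate φ, the difference is D(δ) = D(1) + (δ − 1)·φ·m1/n1, which rises linearly in δ. A significant benefit starts below z = −1.96 and the SAP stops at z = 0. Since z changes continuously with δ, p passes 0.05 strictly before D reaches 0. This needs no planning assumption beyond some missing REGN2222 outcomes.

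**Size, planning case** (one stratum, expected counts, SAP 5.7.1 statistic):

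- REGN2222 events: 0.04 × 380 + δ × 0.10 × 20 = 15.2 + 2δ. Placebo events: 40.
- p* = (events + 0.5)/401; SE² = [p1*(1 − p1*) + p2*(1 − p2*)]/401; z = D/SE.
- δ = 1: D = 17.2/400 − 40/400 = −0.057, z = −3.13, p = 0.0017.
- δ = 4: D = −0.042, SE = 0.0191, z = −2.20, p = 0.028.
- δ = 5: D = −0.037, SE = 0.0194, z = −1.91, p = 0.056.
- p = 0.05 exactly at δ = 4.82 (imputed rate 0.48).
- D = 0 at δ = 1 + 0.057/0.005 = 12.4 (imputed rate 1.24).
- At δ = 10, with every missing REGN2222 infant counted as an event, D is still −0.012 (p = 0.56).

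Four strata with the SAP's weights move the significance crossing only to 4.7. At the original 505 per arm it is 5.6.

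**Other settings, 400 per arm:**

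| Placebo vs REGN2222 rate | Missing | Significance lost at δ | Reversal at δ |
|---|---|---|---|
| 10% vs 4% | 5% | 4.8 | 12.4 (rate above 1) |
| 10% vs 4% | 6.5% REGN2222, 5% placebo | 3.8 | 9.6 |
| 10% vs 4% | 7% | 3.6 | 9.0 |
| 10% vs 4% | 10% | 2.6 | 6.4 |
| 10% vs 5.5% (primary p = 0.025) | 5% | 1.97 | 9.55 |
| 6% vs 2.4% (primary p = 0.018) | 5% | 2.7 (rate 0.16) | 12.4 (rate 0.74) |

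The ratio is 12.4/4.82 = 2.6 in the planning case, 12.4/2.7 = 4.6 in the last row and 9.55/1.97 = 4.8 at 10% vs 5.5%.

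**Simulation.** 100,000 trials per setting; only trials with a significant primary result are counted; whole-number steps; imputed rate held at or below 1; observed placebo completer rate used in place of the Kaplan-Meier estimate.

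| Setting | p ≥ 0.05 reached | Difference ≥ 0 reached |
|---|---|---|
| 10% vs 4%, 5% missing | 88% | 17% |
| 10% vs 4%, 7% missing | 98% | 51% |
| 10% vs 4%, 10% missing | 99.9% | 89% |
| 6% vs 2.4%, 5% missing | 99% | 62% |

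In the planning case 71% of trials lose significance without ever reaching the SAP's stop at a valid rate. When both points are reached, the median steps are 3 versus 7 (10% missing) and 4 versus 13 (6% vs 2.4%).

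**The case against.** The strongest reply is that the SAP states openly what it means by loss of effect and never says that this δ is where significance fails. Reversal of the estimate is a legitimate marker for a descriptive display. Because the primary statistic is run at each step and the loop always passes through the loss of significance, the information is generated anyway. No success criterion uses the analysis.

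Most of this is true, and it limits the seriousness: type I error and the testing hierarchy are unaffected. It does not remove the problem. The SAP shows p-values only as appropriate, does not commit to tabulating every step and does not name the step at which significance goes. The section sets out to assess the primary result, and that result is a significance claim.

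Four further limits stand:

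- The step 3 expression is not legible in the copy reviewed. I read δ as a multiplier of the placebo rate because δ = 1 is stated to equal the primary analysis. A cap may exist in the intact formula. The variance and z-score expressions in 5.7.1 are also damaged, and I read z as difference over standard error.
- The simulated percentages for reversal depend on holding the imputed rate at or below 1, which the readable text does not do. Without a cap the loop would end, but at an impossible rate in the planning case.
- On whole-number steps both points can fall in the same step when much is missing: 4 of 54 significant scenarios tried, all with 30 to 40% missing.
- The size of the gap depends on the scenario; it widens as the primary p-value approaches 0.05.

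**Conclusion.** The concern holds. For any significant primary result with some missing REGN2222 outcomes, the SAP's labelled tipping point lies beyond the δ at which the efficacy conclusion fails. The overstatement is about 2.5-fold under the planning assumptions and nearly 5-fold in the two settings with a primary p-value of about 0.02. In the planning case the stop cannot be reached at a valid imputed rate.

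The direction needs no planning figures. The size rests on 400 per arm, the stated dropout carried over to the reduced design, and the assumed alternative rates. The defect lies in the definition and label of a descriptive analysis, not in the primary inference. It is worth correcting because this is the one analysis that tests the missing-data assumption in the unfavourable direction.

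**What to change.** In SAP 5.7.1.3:

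- Define the tipping point as the smallest δ at which the 2-sided p-value from the primary CMH statistic is at least 0.05.
- Keep a difference of zero or more as a second, separately labelled marker.
- Confirm whether the intact step 3 formula already limits the imputed rate. If not, cap δ times the placebo Kaplan-Meier rate at 1 and report either marker as not reached if the cap comes first.
- For each REGN2222 arm, tabulate δ, imputed rate, estimate, 95% CI and p-value at every step.
- Optionally use finer steps, such as 0.25, since whole steps are coarse when significance is lost near δ = 2.

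The cost is SAP wording, a loop condition and one table per arm. The primary analysis, error control and sample size do not change. The reported tipping point will be smaller, and for a result that is only just significant it may fall at δ = 2 or 3.

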5.7.1.4. Individual Endpoints

The primary efficacy variable can be considered as a composite endpoint comprising the 2 individual endpoints:

- Subjects hospitalized for RSV infection during the 150-day efficacy assessment period.
- Subjects who had outpatient visit (ie, ER, UC, or PC visit) with RSV LRTI during the 150-day efficacy assessment period.

In order to examine which whether an individual endpoint will be driving the treatment difference observed for the primary efficacy variable, each of the 2 individual endpoints will be analyzed using the primary approach for the primary efficacy variable, including handling of missing data (Section 4.6.1) and the CMH statistics (Section 5.7.1). In addition, Fisher's exact test described in Section 5.7.1.2 will be performed for these 2 individual endpoints to confirm the results.

5.7.1.5. Sensitivity to GCP Non-compliance Site

To assess the impact of study data collected from an investigational study site that was not compliant with GCP standards, the primary efficacy analysis will be repeated excluding subject data from the non-compliant site.

5.7.1.6. Sensitivity to Stratification at Randomization

In order to assess the robustness of the primary analysis to stratification mistakes made at the time of randomization (ie, the stratum recorded in IVRS/IWRS differs from the actual stratum recorded in the eCRF), the primary efficacy analysis will be repeated replacing the IVRS/IWRS strata with the eCRF actual strata.

5.7.1.7. Subgroup Analysis

To assess the homogeneity of treatment effect across various subgroups, the primary efficacy variable will be analyzed using the same CMH method as in the primary approach for each subgroup of subjects defined by the following baseline characteristics, risk factors, geographic areas, or enrolment season:

- Race (White, other)
- Chronological age (≤ 3 months, > 3 months)
- Sex (Female, Male)
- Ethnicity (Hispanic or Latino, not Hispanic or Latino)
- Region (NA, rest of the world)

- Gestational age (≤ 31 weeks 6 days GA, ≥ 32 weeks 0 days and < 35 weeks 6 days GA)
- Hemisphere (Northern, Southern)
- Enrollment season (2015-2016 Northern Hemisphere, 2016 Southern Hemisphere, 2016-2017 Northern Hemisphere)
- Study subjects in child care (Yes, No)
- Children, 6 years or younger, live in study subject's household (Yes, No)

For ET subjects those who did not complete Day 150 visit, their primary endpoint will be handled according to the rules used in the primary analysis (Section 4.6.1) before conducting the CMH analysis for each subgroup.

Point estimates and 95% CIs of the treatment effect will be calculated for each subgroup if that subgroup is of reasonable size to perform the evaluation. Since the study sample size is not powered for subgroups, CIs are provided for descriptive purpose. Results for treatment difference in the subgroups of subjects will be graphically displayed in the form of forest plots.

In addition to the CMH statistics, logistic regression will be run with treatment, region, gestational age category, subgroup variable (eg, race), treatment-by-subgroup variable interaction term in the model. The p value of the treatment-by-subgroup variable interaction term will be reported for descriptive purpose to assist the evaluation of treatment effect differentiation across the levels of a subgroup variable.

As small cell size is more likely to occur in subgroup analyses, the Fisher's exact test will be applied to the whole FAS within each subgroup in a similar fashion to the method described in Section 5.7.1.2 with the only difference being that \diamond_i and \diamond_i will be subgroup specific.

5.7.2. Analysis of Secondary Efficacy Variable

The secondary efficacy variable is the proportion of subjects who have RSV-confirmed hospitalization, ER, UC, or pediatric clinic visits (for upper or lower respiratory infection) during the 150-day efficacy assessment period. This secondary endpoint is different from the primary endpoint in the way that the RSV-confirmed outpatient visit (ER, UC, or pediatric clinic visits) for either upper or lower respiratory infection is included as the secondary endpoint event while only the RSV-confirmed outpatient visit for lower respiratory infection is included in the primary endpoint event. The secondary endpoint will be analyzed by the same set of analyses as for the primary efficacy variable including the primary statistical approach, model assumption checks, supportive statistical approaches, individual endpoints, sensitivity analyses, and subgroup analyses.

To understand if REGN2222 can provide any benefit in preventing upper respiratory RSV infection, the proportion of subjects who had observed secondary endpoint event(s) but no observed primary endpoint event(s) will be descriptively summarized for each treatment group.

5.7.3. Adjustment for Multiple Comparison

To control the 5% overall Type I error for the 2 pairwise comparisons in the primary analysis, the overall study α level will be controlled by the use of a hierarchical inferential approach.

Statistical significance of the first pairwise treatment comparison (REGN2222 2 doses arm to placebo) is required before drawing inferential conclusions about the second pairwise treatment comparison (REGN2222 1 dose arm to placebo) at the 0.05 alpha level. This fixed hierarchical approach will ensure a strong control of the overall Type I error rate at the 0.05 level for each REGN2222 dose regimen comparison.

Further, in the case that the primary efficacy endpoint is statistically significant at 0.05 (2-sided) alpha level for both pairwise treatment group comparisons specified in the above paragraph, the secondary efficacy endpoint will be tested using the same hierarchical inferential approach as used for the primary efficacy endpoint.

This multiple testing procedure ensures a strong control of the overall Type I error rate at the 0.05 level. No further adjustments will be made for other analyses for which p-values will be provided for descriptive purpose only.

No adjustment will be made for the first step and second step statistical analyses (Section 8), since the primary and secondary efficacy endpoints will have been concluded at the time of the first step analysis.

5.7.4. Analysis of Exploratory Efficacy Variables

Time to event endpoints

Number of days to the first efficacy endpoint event will be analyzed with stratified log-rank test. Different from the primary analysis, this time to event analysis will treat missing primary endpoint at Day 150 visit through a censoring method as described in Section 4.6.3.

The SAS LIFETEST procedure will be used to run the stratified log-rank test by specifying region and gestational age category in the STRATA statement as 2 stratifying variables, and specifying treatment group in the GROUP= option. In addition, for each treatment group, Kaplan-Meier curve will be used to graphically depict the proportion of subject who remained event free across time during the 150-day efficacy assessment period. Cox regression will be used to obtain hazard ratios and their confidence intervals. The Cox regression model will include the fixed categorical effects of treatment group, region, and gestational age category.

Continuous efficacy endpoints

Descriptive statistics including the number of subjects reflected in the calculation (n), sum, mean, median, SD, minimum, Q1 and Q3, and maximum will be used to summarize the continuous exploratory endpoints (eg, total number of medical visit, length of stay in hospital, etc., as defined in Section 4.6.3) for each treatment group and their treatment difference between each REGN2222 arm and placebo. For each exploratory endpoint, this descriptive summary will include only those subjects who had at least 1 endpoint specific event.

To account for subjects who had no endpoint specific event, a separate analysis will be performed for each exploratory endpoint to include these subjects by treating their endpoint value as zero. In this analysis, the event rate adjusted by subject-year of follow-up will be provided for each treatment group. For each subject, the duration calculated as (end of efficacy evaluation - first dose date +1)/365.25 will be counted toward the subject-year of follow-up, except that for the endpoint of total number of respiratory illness-associated hospital, ER, UC, or PC visits **after** the initial episode of RSV illness, the duration will be (end of efficacy

evaluation - the day after the stop date of the initial episode of RSV illness + 1)/365.25. The end of efficacy evaluation is the last visit completed by a subject, scheduled or unscheduled, up to Visit 7. Negative binomial regression will be used to estimate the relative risk reduction associated with each REGN2222 arm as compared to placebo.

Categorical efficacy endpoints

RSV confirmed hospitalization, a component of the primary composite endpoint, will be explored using the same statistical methodology as the primary efficacy analysis. For this exploratory analysis, the two REGN2222 treatment groups will be combined for comparison to the placebo group, with the intent to evaluate the REGN2222 effect on subjects with RSV confirmed hospitalization.

Number and percentage of subjects taking medications associated with RSV or respiratory illness will be summarized by treatment group. The denominator used to calculate percentage will be the number of subject in the FAS assigned to each treatment group. The tables will be sorted by alphabetical order of ATC level 2 followed by ATC level 4.

The procedures associated with RSV or respiratory illness will only be listed for subjects in each treatment group.

The same CMH statistics as used in the primary approach for the primary efficacy variable will be used to analyze the following exploratory endpoints. Missing data will be addressed using the same same rules as used in the primary analysis for the primary efficacy variable (Section 4.6.1).

- Proportion of FAS subjects with the primary endpoint event, with the single exception of using an alternative definition for LRTI.
- Proportion of subjects with the primary endpoint event, with the single exception of the removal of RSV hospitalization non-LRTI

